Title: An fMRI Study of Stimulant vs. Non-Stimulant Treatment of ADHD

NCT Number: NCT02259517

Document Date: July 10, 2020

Hypothesis Testing

Primary Objective: Vyvanse (lisdexamfetamine; LDX) reduces impulsivity by normalizing cognitive control and reward processing circuits, whereas Intuniv (guanfacine, extended-release; G-EX) reduces impulsivity by normalizing cognitive control but not reward processing circuits.

We will first examine whether there are significant pre- vs. post-treatment changes in cognitive control and reward processing circuits. **Task-based functional MRI (fMRI) analyses:** We will enter each participant's task-related contrast map into a 2×2 repeated measures factorial model, treating Time as a repeated measure with two levels (pre- and post-treatment), and Treatment as a between group factor with two levels (LDX and G-EX). We will isolate an interaction term (Time \times Treatment) to determine differential effects of treatment on task-related activation and then conduct post-hoc t- tests to determine the nature of the interaction. **Resting-state functional connectivity MRI (Rs-fcMRI) and Diffusion Tensor Imaging (DTI):** Analyses will be similar to those for task-based fMRI, but dependent variables will be seed based connectivity and FA maps.

For mediation analysis of treatment effects, we first estimate the changes in cognitive control and reward processing circuits that result from treatment (described in paragraph above). We then establish that the changes in these circuits, in turn, affect impulsivity, while controlling for treatment group. To estimate **path a (Fig. 1)**, we will use a linear regression model with pre-post

[figure not shown]

Figure 1 Mediation Model

changes in cognitive control and reward processing circuits as the outcome variable and treatment as the predictor variable. If we find a significant effect of treatment on both reward and cognitive control circuits, we will pursue multiple mediation analyses; otherwise, we will include only the circuit in which there is a significant effect of treatment. To estimate **path b**, we will use a linear regression model with pre-post change scores in impulsivity (based on parent report) as the outcome and

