pre-post change in cognitive control or reward processing circuits as primary predictors, while controlling for baseline impulsivity and treatment group. The mediation effect is then estimated by taking the product of the estimates for **path a and b** and using the bootstrap method to obtain standard errors, confidence intervals, and the test for statistical significance.

To test whether treatment effects on cognitive control or reward processing circuits are specific in mediating improvements in impulsivity, we will explore whether treatment-related changes in other neural networks also mediate the effect of treatment on impulsivity. We will first screen these additional neural networks based on a significant effect of treatment on connectivity within these networks. Only networks that show significant change with treatment will be added to the multiple mediation analyses described above. The indirect effects of the cognitive control or reward processing circuits will be tested in the existence of the mediation effects of other neural networks using the bootstrapping method.

Power: Power for detecting the mediation effect depends on the size of the associations between (a) treatment group and changes in cognitive control and reward processing circuits, and (b) changes in cognitive control and reward processing circuits and changes in impulsivity. Based on tabulated recommendations for sample sizes needed to test mediation effects, with a sample size of $n=60$, we have more than 80% power to detect a significant mediation effect with medium effect size of both paths a and b.

Secondary Objective: ADHD patients with baseline MRI anomalies within reward processing circuits will respond to Vyvanse, but not Intuniv, treatment. Conversely, ADHD patients with baseline MRI anomalies that are circumscribed to cognitive control circuits (i.e., reward processing comparable to healthy controls) will predict response to either Intuniv or Vyvanse.

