We will test the moderation effect of the baseline MRI measures cognitive control and reward processing circuits on the treatment response. We will use linear regression models with pre-post change scores in impulsivity measures as outcomes and Group, baseline measures of cognitive control and reward processing circuits measured in predefined regions of interest (ROIs), and their interactions as predictors. Likelihood ratio tests will be used to test the effect of moderation with combination of multiple brain imaging measures.

Power: With sample size of $n=60$, the minimum detectable effect size of Cohen's f^2 is 0.09 (smaller than medium effect size 0.15) with 80% power for a two-sided test at the 5% significance level. If the effect size of interactions between baseline measures within cognitive control and reward processing circuits and Group is greater than f^2 is 0.09, we would be able to detect such effect size.

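### Path a and the Time × Treatment test compare raw circuit change without the baseline circuit value; adjusting for it would sharpen the between-arm contrast unless the pre-post correlation is high

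*SAP*

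**What the plan says.** All of this stands in the SAP under Primary Objective.

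- **Task fMRI.** Contrast maps enter a repeated-measures factorial model, "treating Time as a repeated measure with two levels (pre- and post-treatment), and Treatment as a between group factor". The Time × Treatment interaction is isolated and followed by post-hoc t-tests.
- **Resting-state connectivity and DTI.** "Analyses will be similar to those for task-based fMRI, but dependent variables will be seed based connectivity and FA maps".
- **Path a.** A linear regression has pre-post "changes in cognitive control and reward processing circuits as the outcome variable and treatment as the predictor variable". Treatment is the only predictor named. Only a circuit with a significant treatment effect goes forward to mediation.
- **Path b.** Change in impulsivity is regressed on change in the circuit, "while controlling for baseline impulsivity and treatment group". The baseline circuit value is not named here either.

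Baseline circuit measures appear as predictors only in the Secondary Objective's moderation model, whose outcome is change in impulsivity and which uses predefined regions of interest. The Protocol (Study Procedures) has every participant scanned at baseline and randomises the ADHD participants 1:1 without blinding.

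**The concern.** Regressing change on treatment alone fixes the coefficient of the baseline value at 1. Unless the measure is highly stable between scans, that over-corrects: noise in the first scan is carried in full into the change score. In a randomised comparison, letting the data estimate that coefficient targets the same treatment effect with a residual variance that is no larger in large samples.

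The loss matters because path a acts as a filter. A circuit that misses significance there is dropped from the mediation analysis, and other networks are screened in the same way. The primary objective predicts that the arms differ on reward processing, while both drugs normalise cognitive control. The reward path therefore has most to gain from a sharper between-arm contrast.

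**Working it through.** **Inputs.** From the documents: 1:1 allocation (Protocol, Randomization Procedures); n=60 (SAP, both Power paragraphs); 30 children with ADHD (Protocol, Lay Summary, and as required completers under Description of Subject Population); medium f² = 0.15, two-sided 5% (SAP, Secondary Objective, Power). Assumed, because the documents give no value: the pre-post correlation rho, the pre and post SDs (s1, s2), and a between-arm difference of 0.5 baseline SD for illustration.

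**The plan's own figure.** The SAP gives no precision or power for path a alone. Its nearest statement is for the whole mediation effect: "with a sample size of $n=60$, we have more than 80% power to detect a significant mediation effect with medium effect size" of both paths. If medium means f² = 0.15 on each path, simulation at n=60 gives about 68% by joint significance, 67–68% by percentile bootstrap and 76–77% by bias-corrected bootstrap. The figure does not reproduce on that reading. The SAP's tabulated source may define medium otherwise, and nothing below depends on it.

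**Step 1: the two models are one test.** With two time points, the Time × Treatment contrast is the mean change in one arm minus the mean change in the other, which is a two-sample t-test on change. Path a is the same comparison written as a regression.

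**Step 2: variances.**
- Raw change: s1² + s2² − 2·rho·s1·s2.
- Baseline-adjusted: s2²(1 − rho²).
- Difference: (s1 − rho·s2)², never negative.

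With s1 = s2 the ratio is 2(1 − rho)/(1 − rho²) = 2/(1 + rho).

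**Step 3: extra children that raw change needs.** Chance baseline imbalance inflates the adjusted variance by 1 + 1/(N − 4), which is 57/56 at N=60 and 27/26 at N=30. For example, at rho = 0.5 and N=60: 1.333 × 56/57 = 1.310, or 31%.

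| rho (assumed) | 2/(1+rho) − 1 | N=60 | N=30 |
|---|---|---|---|
| 0.3 | 54% | 51% | 48% |
| 0.5 | 33% | 31% | 28% |
| 0.7 | 18% | 16% | 13% |
| 0.8 | 11% | 9% | 7% |
| 0.9 | 5% | 3% | 1% |

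Setting 2/(1 + rho) equal to the inflation factor gives break-even at rho = 0.96 for N=60 and 0.93 for N=30.

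**Step 4: unequal SDs, at rho = 0.7.** If s2/s1 = 1.2, the variances are 1 + 1.44 − 1.68 = 0.76 and 1.44 × 0.51 = 0.734, ratio 1.03. If s2/s1 = 1.4, they are 1.00 and 1.96 × 0.51 = 1.00, so the gain vanishes.

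**Step 5: power for a 0.5 SD difference** (noncentral t, two-sided 5%, equal SDs, inflation factor included; raw change on N − 2 df, adjusted on N − 3).

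| rho | N=60, raw → adjusted | N=30, raw → adjusted |
|---|---|---|
| 0.3 | 36% → 51% | 20% → 27% |
| 0.5 | 48% → 59% | 26% → 32% |
| 0.7 | 69% → 75% | 40% → 44% |

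**Step 6: the same on the SAP's scale.** Take f² = 0.15 as path a's effect on raw change. Noncentrality is 60 × 0.15 = 9 on 1 and 58 df, and power is 84%. Adjustment multiplies f² by the N=60 ratio from Step 3: 0.15 × 1.51 = 0.227, 0.15 × 1.31 = 0.196 and 0.15 × 1.16 = 0.173. Power on 1 and 57 df becomes 95%, 92% and 89% at rho 0.3, 0.5 and 0.7.

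**The case against.** The strongest reply is that nothing here is wrong. Under 1:1 randomisation the comparison of raw change is unbiased and its test is valid. That stands. A reader might infer that leaving out the baseline invalidates or biases path a; the documents do not support this.

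A reader might also take 18–54% as a property of this trial. It is not. It is a formula evaluated at assumed correlations with equal SDs, and task activation, seed connectivity and FA may each have a different rho. Nor is adjustment better at every rho below 1 in a small sample, as the break-even values show. The 0.5 SD power figures are likewise illustrative: on the SAP's own f² scale, path a alone already has about 84% power at n=60.

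It is tempting to replace the 2×2 model outright. That would drop a planned analysis. The SAP first asks whether circuits change from before to after treatment, and the Protocol's Hypothesis 1b concerns change after either drug. The Time effect and the post-hoc tests answer those questions; a baseline-adjusted between-arm model does not.

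Finally, with different covariates in paths a and b, the product a × b will not equal total minus direct effect in the sample. This has little consequence, because the SAP bootstraps the product and never uses that decomposition.

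**Conclusion.** The point holds as a matter of efficiency. Path a and the Time × Treatment term leave unused a baseline measurement that the trial already collects, in the step that decides which circuits enter mediation. If rho lies between 0.3 and 0.7 and the SDs are equal, raw change costs the equivalent of 51% to 16% more children at N=60, or 48% to 13% at N=30. The gain is about 9% or less at rho 0.8 to 0.9, and near zero if the post-treatment SD is about 1.4 times the baseline SD at rho 0.7. The direction is secure in large samples. The size cannot be fixed from the documents. The change is worth making because it costs little, not because the present analysis is unsound.

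**What to change.** 1. In the region-of-interest path a, keep circuit change (or the post-treatment value) as outcome and treatment as predictor, and add the baseline value of the same circuit.
2. Carry the same baseline circuit term in path b, alongside baseline impulsivity and treatment, so that both paths refer to circuit change at a given baseline.
3. Keep the 2×2 repeated-measures model for the pre-post Time effect and the post-hoc tests. Base the between-arm contrast on the baseline-adjusted model, using region summaries or the baseline map as a voxelwise covariate.
4. If the SAP quotes a gain, give it as 2/(1+rho) − 1 and state rho and the SD ratio as assumptions.

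The cost is SAP wording, settled before any comparison by arm because treatment is open. It takes one degree of freedom per circuit baseline, hence two if both circuits enter a multiple-mediator model, which counts for more with 30 children than with 60. The map-level model becomes somewhat more complex. If rho proves very high, there is little or no gain.

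### The LDX-versus-G-EX mediation model can show only differential mediation, and its inclusion rule can bias the reward path when cognitive control is dropped

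*SAP*

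**What the plan says.** Under Primary Objective, the SAP holds that LDX works through both circuits, whereas G-EX "reduces impulsivity by normalizing cognitive control but not reward processing circuits". Cognitive control is therefore the shared mechanism, and reward is the one that distinguishes the drugs.

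The imaging model takes "Treatment as a between group factor with two levels (LDX and G-EX"). Path a is a linear regression with "changes in cognitive control and reward processing circuits as the outcome variable and treatment as the predictor variable". The power paragraph for the same objective also describes path a as the association between "treatment group and changes in cognitive control and reward processing circuits".

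If both circuits show a significant treatment effect, a multiple mediation model follows; "otherwise, we will include only the circuit in which there is a significant effect of treatment". Path b regresses the change in parent-reported impulsivity on "pre-post change in cognitive control or reward processing circuits as primary predictors, while controlling for baseline impulsivity and treatment group". The mediation effect is the product of a and b, tested by bootstrap.

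Other planned steps bear on this. The SAP opens with: "We will first examine whether there are significant pre- vs. post-treatment changes in cognitive control and reward processing circuits". It also says, before giving the inclusion rule, that it will show the circuit changes influence impulsivity with treatment group adjusted for. The protocol (Lay Summary; Hypothesis 1b) compares the second scan with the first and with healthy controls.

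**The concern.** There are two separate problems.

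**What is estimated.** With two active arms and no other treatment level, path a is a between-drug contrast. A mechanism that both drugs share to the same degree has a = 0, so a × b = 0 however strongly the circuit drives impulsivity. The analysis named for the primary objective cannot support its shared half, and an absent or null cognitive-control result could be taken as evidence against it.

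**What is omitted.** If cognitive control fails the inclusion rule, reward path b is fitted without a variable that the SAP itself expects to affect impulsivity. Adjusting for arm does not help, because the correlation that matters lies within arm. The reward indirect effect, which is meant to separate the drugs, may then be inflated, created or masked.

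**Working it through.** **Inputs from the documents.** Two treatment levels, 1:1 allocation; n=60 (SAP power paragraphs); 30 ADHD completers (protocol, Description of Subject Population). Both sizes are shown. Medium is f² = 0.15 and the test is two-sided 5%; the SAP states both only under its secondary objective. With unit SDs, f² = 0.15 gives b = √0.15 ≈ 0.39.

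**Assumed, not in the documents.** Residual SD 1; reward difference between arms d about 0.8 (0.78 to 0.80 across runs); within-arm correlation ρ of the two circuit changes from −0.5 to +0.5.

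**The plan's own figure.** The SAP states more than 80% power for mediation at n=60 with medium paths. With f² = 0.15 on each path, power is 0.839 for a and 0.838 for b, and 0.839 × 0.838 = 0.70. The stated figure is not reproduced at two-sided 5%, but this point does not depend on it. It matters here only because it treats path a as a treatment-group association.

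**Step 1: shared mechanism.** With a = 0 for cognitive control, both circuits entered, and a real cognitive-control effect on impulsivity (b = 0.39 or 0.6), the percentile bootstrap of its a × b is significant in 2.0–4.7% of trials (n=30) and 3.3–6.3% (n=60). That is roughly the false-positive rate, although the circuit truly matters.

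**Step 2: how often the rule drops cognitive control.** Two-sample t test, noncentrality d√(n/4):
- d = 0: 95% at either size.
- d = 0.5, n=60: 0.5 × √15 = 1.94, dropped in 52%.
- d = 0.5, n=30: 0.5 × √7.5 = 1.37, dropped in 74%.

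**Step 3: effect on reward path b.** Omitting cognitive control gives an expected coefficient of b_R + b_C × ρ × (SD_C/SD_R). With both b = 0.39 and equal SDs, this is 0.39 + 0.39 × 0.5 = 0.585 at ρ = +0.5, 0.39 at 0, and 0.39 − 0.195 = 0.195 at −0.5. Simulation with the inclusion rule applied (20,000 to 40,000 trials per setting, no between-drug difference in cognitive control) agrees:

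| ρ | Mean reward b (true 0.39) | False significance, n=30 | False significance, n=60 |
|---|---|---|---|
| +0.5 | 0.59 | about 13–15% | about 27–28% |
| +0.3 | 0.51 | about 8% | about 13% |
| 0 | 0.39 | 5% | 5% |
| −0.3 | 0.27 | about 8% | about 13% |
| −0.5 | 0.19–0.20 | about 13–15% | about 27–28% |

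The last two columns take no true reward effect and b_C = 0.39, in trials where reward alone passes. Reward alone passes in about 51% (n=30) and 81% (n=60) of trials. Over all trials at ±0.5 the rate is therefore about 0.51 × 0.145 = 7% and 0.81 × 0.273 = 22% (7–8% and 22–23% across runs).

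With a true reward effect and ρ = −0.5, path b power where reward alone passes falls from 36% to 15% (n=30) and from 69% to 28% (n=60).

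**Step 4: both circuits entered.** Mean reward b is 0.39 when the truth is 0.39, at every ρ tried, and the false-positive rate is about 5%.

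**The case against.** **The shared circuit is not ignored.** The SAP tests pre-post change first and says it will show that circuit changes affect impulsivity. Path b, being adjusted for arm, is already a pooled within-arm association. This stands in part: a reader might infer that the plan has no analysis of cognitive control at all, and the documents do not support that. But the pre-post tests show only that the circuit changed, and the operational path b follows the inclusion rule.

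**The rule may mean something looser.** The SAP speaks of circuit changes "that result from treatment (described in paragraph above"), and that paragraph includes the pre-post step. If circuits are kept on pre-post change, a 0.5 SD pooled change is dropped in only 3% of trials at n=60 and 25% at n=30. The dropping harm is then much smaller, although the meaning of a × b is unchanged. The path a and power wording favours the between-drug reading.

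**The bias is conditional.** It is tempting to say that the rule does bias, or always inflates, the reward path. Neither is supported: bias needs a non-zero within-arm correlation, its sign follows that correlation, and at zero there is none.

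**Causal order.** If cognitive-control change is downstream of reward change (slope 0.5), the reward-only model recovers the total effect, 0.39 + 0.5 × 0.39 = 0.585, while entering both gives the direct effect, 0.39. The documents do not settle the order, so this stands and the fix must state its assumption.

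**Larger rates.** Setting b_C = 0.6 raises conditional false significance to about 26% (n=30) and 50% (n=60) at ±0.5. That is f² = 0.36, more than twice the SAP's medium, so it is a sensitivity case only.

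**Conclusion.** The concern holds in two parts of different strength.

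The limit on a × b follows from the two-level treatment factor and needs no assumed effect size or correlation. The analysis can show differential mediation and cannot test the shared half of the primary objective. A reader might go further and treat a null cognitive-control result as evidence against that half. Nothing in the documents supports this, since a null is what equal action would produce.

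The inclusion rule can also bias reward path b. At the SAP's medium effect the illustrative shift is up to about ±50% of the true coefficient at |ρ| = 0.5 (0.195/0.39). With no true reward effect, false significance is about 13–15% (n=30) and 27–28% (n=60) in the affected trials. This rests on the between-drug reading of the rule, cognitive-control change affecting impulsivity, a non-zero ρ, and the assumed reward d.

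This should be fixed before analysis. It does not make the trial uninformative. The lack of a controlled test of the shared mechanism comes from having two active arms and no rescanned untreated group; no SAP edit supplies one.

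**What to change.** 1. Replace the inclusion rule with: *Pre-post change in cognitive control and in reward will both be entered in path b whatever the result of path a, and both indirect effects will be reported with bootstrap intervals.* State the assumption that cognitive-control change is not downstream of reward change. If it is, the reward estimate is a direct effect, so also report the reward-only model as a sensitivity analysis.
2. State that the LDX-versus-G-EX indirect effect supports only differential mediation, and that a non-significant cognitive-control path a or indirect effect is not evidence against a shared mechanism.
3. For the shared mechanism, report pre-post change in cognitive control in each arm together with its arm-adjusted path b coefficient, and by-arm estimates with intervals. Label these supportive and uncontrolled.

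**Cost.** SAP wording, a few model fits on planned data, one degree of freedom, and slightly wider intervals when the circuit changes correlate. With both entered and b = 0.39, reward path b power is 48% (n=30) and 80% (n=60) at ρ = 0, and 38% and 69% at ±0.5. Joint-significance power at ρ = 0 is 26% and 69%, against 24% and 65% under the current rule, so nothing is lost there.

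The by-arm estimates will be imprecise. With 15 per arm, mean change is known to ±0.55 SD (2.145/√15), and an observed correlation of 0.5 has a Fisher z interval of −0.02 to 0.81. With 30 per arm these become ±0.37 SD and 0.17 to 0.73.

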Children with Attention-Deficit/Hyperactivity Disorder (ADHD) are typically treated with two types of medications with differing mechanisms of action: stimulants and non-stimulants. The stimulant Vyvanse (lisdexamfetamine, LDX), and the non-stimulant Intuniv (extended-release guanficine, GXR), are both FDA-approved treatments for ADHD in children. Clinical trials have shown that both medications are effective in reducing ADHD symptoms, although the neurobiological mechanisms by which Vyvanse and Intuniv produce these effects remain unknown. The aim of this study is to examine the mechanisms by which LDX and GXR reduce symptoms in children with ADHD. MRI scanning will be used to understand the structure and blood flow within the brains of children with ADHD treated with LDX and GXR.

A total of thirty (30) children with ADHD and ten (10) age- and sex-matched, healthy controls will be scanned at the beginning of the study. In this first part of the study, MRI findings will be compared between the groups (i.e., children with and without ADHD) to see whether brain functioning of children with ADHD differs from that of healthy children. In the second part of the study, the children with ADHD will be randomized (1:1 ratio) to receive treatment with LDX or GXR for six (6) weeks. In the first few visits of the treatment phase of the study, the study doctor may adjust the medication dose to optimize its effect. At the end of the study, the children with ADHD treated with LDX or GXR will have a second MRI scan. The findings of that second MRI scan will be compared to the first MRI scan in order to identify brain changes due to the medication. These second MRI scans will also be compared to the scans of the healthy controls.

We seek to examine whether treatment with LDX and GXR leads to changes in brain structure and function and thereby help to reduce symptoms of ADHD. Furthermore, we will examine how these two drugs differ in yielding their therapeutic effect. This may inform how specific changes in the brain may underlie improvement in the various symptoms of ADHD.

Background, Significance and Rationale

Background, Significance and Rationale

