- **For ADHD participants with a history of tic disorder:** Based on the information gathered from the medical history and the psychological assessments during the initial visit(s), the study doctor will carefully weigh the risks and the benefits of LDX treatment with the parent/guardian of the child participant. The decision to randomize the participant or to remove him/her from the study will depend on the study doctor's clinical judgment and the preferences of the parent/guardian. The study doctor will follow the same clinical practice guidelines for evaluating and treating co-occurring ADHD and tic disorder as doctors in the community. If the study doctor and parent/guardian agree that the benefits of potential treatment with LDX outweigh the risks, then the participant will proceed to the randomization procedures outlined below.
- **For female ADHD participants who have had their first period:** Female ADHD participants who have had their first period and who are sexually active will need to: (1) be using contraception prior to beginning treatment, and (2) agree to continue using contraception throughout the course of treatment in order to participate in the study. The study doctor will talk to female participants who have had their first period about ways to prevent pregnancy, the potential risks of the study medications on pregnancy (as part of consent/assent), as well as the limitations of urine pregnancy testing. Participants and their parents/guardians will be advised to notify the researcher immediately should they suspect that the participant is pregnant. If a participant is suspected to be pregnant, we will perform another pregnancy test to determine if she should continue the study. In case of pregnancy, the participant will discontinue the study early and we will provide assistance with obstetrical follow-up.

2. Randomization Procedures

Eligible ADHD participants will be randomized to treatment with LDX or GXR using a 1:1 ratio. Participants, research staff, and the study doctor will NOT be blinded to treatment.

3. Medication Management

Following randomization, participants will be taken through a medication management protocol over the subsequent 6 weeks. This protocol will begin with 4 weeks of medication titration, which will be followed by 2 weeks of medication maintenance. Titration will help the study doctor determine the minimum dose of medication necessary to achieve treatment response.

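### The specificity analysis admits a competing network only if its own treatment effect is significant, so a target circuit can be credited with another network's effect

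*SAP*

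**What the plan says.** Under Hypothesis Testing, Primary Objective, the SAP estimates mediation as the product of path a (treatment to circuit change) and path b (circuit change to change in impulsivity, adjusted for baseline impulsivity and treatment group), "using the bootstrap method to obtain standard errors, confidence intervals, and the test for statistical significance".

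It then turns to specificity: "we will explore whether treatment-related changes in other neural networks also mediate the effect of treatment on impulsivity". Competitors have to pass a gate: "We will first screen these additional neural networks based on a significant effect of treatment on connectivity within these networks". The consequence is explicit: "Only networks that show significant change with treatment will be added to the multiple mediation analyses described above". The targets' indirect effects are then tested alongside whatever passed.

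The SAP does not name the comparison networks, give a significance level or multiplicity rule for the gate, or state what result would count as specific. The two gate sentences also differ: one speaks of an effect of treatment, the other of change with treatment. The gate could therefore be a between-arm test or a pre-post test.

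**The concern.** A specificity analysis asks whether the target's indirect effect survives when plausible competitors are held constant. Here a competitor is held constant only if its own treatment effect is significant in the same small sample. If none passes, the specificity model is simply the primary mediation model again, and nothing has been tested.

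The gate also uses the wrong criterion. Treatment is randomised, but circuit change is not. Path b is therefore open to confounding by any network whose change correlates with the target's change and which affects impulsivity. That bias does not depend on the competitor's path a. At stake is the mechanistic conclusion of the primary objective: another network's effect may be attributed to cognitive control or reward circuits.

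**Working it through.** **Inputs from the documents.**
- SAP power paragraph for mediation: "with a sample size of $n=60$, we have more than 80% power to detect a significant mediation effect with medium effect size" for both paths. It gives no number for medium.
- The only numerical medium effect is in the secondary objective's power paragraph: "smaller than medium effect size 0.15) with 80% power for a two-sided test at the 5% significance level". I carry f² = 0.15 and two-sided 5% over to mediation and to the gate as an assumption.
- Protocol, Randomization Procedures: "Eligible ADHD participants will be randomized to treatment with LDX or GXR using a 1:1 ratio".
- Protocol, Lay Summary: "A total of thirty (30) children with ADHD and ten (10) age- and sex-matched, healthy controls will be scanned". The Description of Subject Population also requires 30 ADHD completers. Only ADHD children are treated, so I show both n = 60 and n = 30.

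**The plan's own figure first.** With 1:1 allocation f² = d²/4, so d = 2√0.15 = 0.775. At n = 60, two-sided 5%, path a power is 83.9% and path b power 83.8%. The product is 0.839 × 0.838 = 0.703. A simulated percentile bootstrap of a×b gives 68% and a bias-corrected one 76%. The stated power of more than 80% is not reproduced on these assumptions; one-sided 5% testing gives 82.2%. What matters for the gate is the path a power.

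**How often the gate drops a real competitor.** The probability is 1 − power of a two-sample t test, with noncentrality d√n/2:

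| n treated | d | d√n/2 | critical t | dropped |
|---|---|---|---|---|
| 60 | 0.775 | 3.00 | 2.00 | 16% |
| 60 | 0.5 | 1.94 | 2.00 | 52% |
| 30 | 0.775 | 2.12 | 2.05 | 47% |
| 30 | 0.5 | 1.37 | 2.05 | 74% |

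Half are dropped at d = 0.51 (n = 60) or d = 0.74 (n = 30). With Bonferroni correction over five networks, the n = 60 figures become 37% and 76%. If the gate is instead a pooled pre-post test, a standardised change of 0.5 is detected 97% of the time at n = 60 and 75% at n = 30.

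**Why path a is the wrong criterion.** Within arm, omitting the competitor shifts the target's slope by (competitor slope) × (correlation) × (SD ratio). With slope 0.5, correlation 0.5 and equal SDs, the shift is 0.5 × 0.5 × 1 = 0.25; at correlation 0 it is 0. The competitor's path a does not appear. In the extreme, a competitor with no between-arm effect is dropped 95% of the time. At 30 per arm, path b of an inert target is then falsely significant in 17% of trials at correlation 0.3 and 39% at 0.5, against 5% with the competitor included (path b alone, not mediation).

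**False mediation by an inert target.** The documents give no competitor effect, correlation or slope. I assume a target moved by treatment at d about 0.8 with no effect on impulsivity, competitor slope 0.5 and residual SD 1. There were 3,000 trials per setting, and both target paths had to be significant.

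| n | competitor d | correlation | with gate | competitor always in |
|---|---|---|---|---|
| 60 | 0.5 | 0 | 5% | 5% |
| 60 | 0.5 | 0.3 | 10% | 5% |
| 60 | 0.5 | 0.5 | 19% | 4% |
| 60 | 0.5 | 0.6 | 24% | 4% |
| 60 | 0.775 | 0 to 0.6 | 4% to 8% | 4% |
| 30 | 0.5 | 0 to 0.6 | 2% to 12% | 2% to 3% |

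Repeat runs differ by about a point. A separate percentile-bootstrap simulation used slope 0.39, target d = 0.775, competitor d = 0.5 and n = 60. It counted trials in which the inert target was significant and the competitor was not: 13.0% with the gate against 2.0% without at correlation 0.5, and 4.7% against 4.5% at correlation 0.

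**What removing the gate does not cure.** In the same bootstrap setting, when target and competitor both truly mediate, the target alone is significant in 42%, 46% and 52% of trials with the gate (correlation 0, 0.3, 0.5). Without it the figures are 40%, 37% and 39%. Most of that is low power for the competitor's indirect effect.

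**The case against.** The strongest reply is that the analysis is worded as exploratory, that the SAP never says specificity will be declared when no network passes, and that screening limits the number of predictors in a small sample. On the SAP's own n = 60 and f² = 0.15, a real competitor is kept 84% of the time. The inflation also depends on correlations that the documents do not give, and it vanishes when the networks are uncorrelated.

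Much of this stands, and it rules out stronger readings that a reader might infer:
- That real competitors are usually dropped. At n = 60 this needs a competitor effect below about d = 0.51, at n = 30 below about d = 0.74, or a multiplicity correction in some settings.
- That specificity will be claimed too often. The SAP contains no rule for claiming it.
- That false mediation grows as power falls. More competitors are dropped at n = 30, but false mediation is lower there (at most about 12%, against 24% at n = 60), because the target's own paths are also less often significant.

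The remaining defences are weaker. The SAP introduces this step as a test of specificity within its primary objective, and the lack of a decision rule makes it easier to read non-significance as absence. Entering comparison networks one at a time deals with the predictor count without a gate.

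**Conclusion.** The point holds as a bias in a stated rule. Followed as written, the gate can leave a correlated network that truly drives impulsivity out of the target's path b model, and its effect is then credited to the target. The loss of real competitors is 16% to 52% at n = 60 and 47% to 74% at n = 30 for d from 0.775 to 0.5, assuming an uncorrected two-sided 5% between-arm test. The resulting false mediation ranges from no excess at correlation 0 to about 20 percentage points (24% against 4%) at correlation 0.6 with n = 60 and competitor d = 0.5. It is much smaller if the competitor's effect is as large as the target's. These rates rest on assumed slopes, correlations and residual variance; only the direction of the bias and the drop rates for a given d and n are free of those three assumptions. The size also depends on whether 60 or 30 children are treated, which the two documents should reconcile.

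**What to change.** - Delete the significance screen for comparison networks.
- Name a short list of comparison networks in the SAP before the data are examined.
- Enter each beside the target circuits, one at a time, whatever its path a p-value.
- Base any statement on specificity on the bootstrap confidence interval for the difference between the target's and the comparison network's indirect effects, never on a network's failure to reach significance.

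The change needs SAP wording, a decision on which networks to list, and one extra predictor per model with slightly wider intervals. It needs no new data. It does not cure low power for a competitor's own indirect effect, but the interval for the difference will show that as imprecision.
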